#### **Sensitivity Analyses**

Sensitivity analyses will include the following:

- Complete cases: The principal analysis will be repeated using NC=M, i.e., subjects who have missing pain level in the 2-hour post-dose analysis window are excluded. First, the RM=F method of handling intervening rescue medication use will be applied. Next, subjects with missing data in the 2-hour analysis window will be excluded. The same statistics as the principal analysis will be presented.
- Multiple imputation: The principal analysis will be repeated using the copy from reference multiple imputation approach with m=20 imputations to impute missing pain data at 2 hours post-dose. The fully conditional specification (FCS) method is used with a generalized logit distribution. Covariates may include prophylactic migraine medication use at randomization (yes or no), sex, pain level at on-study migraine attack onset (moderate or severe), historical number of moderate to severe migraine attacks per month (< median, ≥ median), and MBS at on-study migraine attack onset (nausea, phonophobia, or photophobia). First, the RM=F

method of handling intervening rescue medication use will be applied. Next, missing data in the 2-hour post-dose analysis window will be imputed for subjects who are not missing any of the covariates (subjects missing any of the covariates will be considered failures). The same statistics as the principal analysis will be presented.

• Varying response rate imputation: The principal analysis will be repeated by imputing missing pain data at 2 hours post-dose in each treatment group with varying response rates over the range of 0%, 10%, 20% and 30%. First, the RM=F method of handling intervening rescue medication use will be applied. Next, missing data in the 2-hour post-dose analysis window will be imputed. The following statistics will be presented: stratified percentage difference between treatment groups (BHV-3500 – placebo), ASE, 98.3% CI, and p-value.

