# 7.6.3.2 Migraine Characteristics

The following migraine characteristics will be collected at migraine attack onset in the eDiary Migraine Report and post-dose from 15 minutes through 48 hours (e.g., 15, 30, 45, 60, and 90 minutes; 2, 3, 4, 6, 8, 24 and 48 hours) in the eDiary Post-Dose Migraine Report:

- Pain level (none, mild, moderate, severe)
- MBS (nausea, phonophobia, photophobia) in the Migraine Report only
- Nausea status (present, absent)
- Nausea level (none, mild, moderate, severe)
- Phonophobia status (present, absent)
- Phonophobia level (none, mild, moderate, severe)
- Photophobia status (present, absent)
- Photophobia level (none, mild, moderate, severe)
- Functional disability level (normal, mildly impaired, severely impaired, requires bedrest)
- Aura (yes, no) in the Migraine Report only.

The eDiary will allow subjects to report one result per time point per migraine characteristics parameter.

In general, if subjects answered "no" to taking study medication mistakenly already, had current pain level of moderate or severe, and did not use other headache medications, then the eDiary Migraine Report will collect all parameters listed above.

Otherwise, if subjects answered "yes" to taking study medication mistakenly already, then the eDiary Migraine Report will not collect the following parameters: most bothersome symptom, current pain level, nausea status, phonophobia status, and photophobia status. Instead, if the subject provided the time of study medication taken, then the eDiary Migraine Report will collect nausea level, phonophobia level, photophobia level, pain level and functional disability level at the time study drug was taken. Thus, for these subjects at on-study migraine attack onset, a symptom status (nausea, phonophobia, photophobia) of absent is defined as a level of none, and present is defined as a level of mild, moderate, or severe.

Windows for post-dose efficacy measurements (15, 30, 45, 60, 90 minutes; 2, 3, 4, 6, 8, 24, and 48 hours) will be automatically assigned by the eDiary as shown in Table 5.

Table 5: eDiary Automated Efficacy Analysis Windows

Post-Dose Evaluation	Analysis-Specified Interval	Target Time
15 minutes	10 to 20 minutes	Study medication start time + 15 minutes
30 minutes	25 to 35 minutes	Study medication start time + 30 minutes
45 minutes	40 to 50 minutes	Study medication start time + 45 minutes
60 minutes	55 to 65 minutes	Study medication start time + 60 minutes

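### If onset MBS stays in the pain-freedom imputation model, subjects who dosed before opening the diary and lack a 2-hour score are still scored as failures, so the multiple imputation does not relax NC=F for them

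*SAP*

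**What the plan says.** SAP Section 6.3.3.1 (Sensitivity Analyses, multiple imputation) repeats the principal analysis of pain freedom with copy-from-reference imputation and 20 imputations. "The fully conditional specification (FCS) method is used with a generalized logit distribution". Rescue use is first set to failure (RM=F). Then "missing data in the 2-hour post-dose analysis window will be imputed for subjects who are not missing any of the covariates", and in parentheses "subjects missing any of the covariates will be considered failures".

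The covariate list is permissive. It opens "Covariates may include prophylactic migraine medication use at randomization (yes or no" and goes on to sex, onset pain level, historical attack frequency and onset MBS.

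SAP Section 7.6.3.2 lists "MBS (nausea, phonophobia, photophobia) in the Migraine Report only", so onset MBS has no second source. For a subject who answers yes to having mistakenly taken study drug already, "then the eDiary Migraine Report will not collect the following parameters: most bothersome symptom, current pain level, nausea status, phonophobia status, and photophobia status". If that subject gives a dosing time, pain level at dosing is still recorded.

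SAP Section 3 admits to mITT a treated subject with moderate to severe onset pain and any dated post-dose efficacy entry. Onset MBS is not required.

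**The concern.** SAP Section 6.1.1 says that the sensitivity analyses of the co-primary endpoints will either leave out subjects with missing data or impute by a different method from the principal one. The principal rule is NC=F: a missing 2-hour pain score is a failure. For a subject without onset MBS and without a 2-hour score, the multiple imputation does neither of these things and applies NC=F again.

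This group is created by the diary's design. Dosing before opening the diary removes onset MBS, and a subject who first opens the diary after the 2-hour window has closed (2 hours 15 minutes) cannot supply a 2-hour score either. The two gaps may therefore tend to occur together. That is an inference; the documents give no counts.

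Pain freedom does not depend on which symptom was most bothersome. For MBS freedom a missing onset MBS is a failure by endpoint definition (SAP Section 6.3.3.2), but that reason does not carry over to pain freedom. What is at stake is whether the multiple imputation tests the assumption that it was added to test.

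**Working it through.** **1. The plan's own figure.** Inputs from SAP Section 5: 380 mITT subjects per arm, 22% versus 12%, alpha 0.0167, taken as two-sided (critical z = 2.393).
- Pooled rate 0.17; null SE = √(2 × 0.17 × 0.83 / 380) = 0.02725.
- Alternative SE = √((0.22 × 0.78 + 0.12 × 0.88) / 380) = 0.02701.
- Power = Φ((0.10 − 2.393 × 0.02725) / 0.02701) = Φ(1.288) = 90.1%.

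The stated 90% is reproduced. The point does not challenge it; these inputs are used below only for scale.

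**2. One subject followed through the SAP.** The subject doses, opens the diary later, reports the earlier dose with its time, and rates pain at dosing as moderate. There is a later post-dose entry but none in the 2-hour window, and no rescue medication up to that window.
- Section 3: in mITT.
- Section 7.6.3.2: onset MBS not collected.
- Section 6.3.3.1, principal analysis: failure (NC=F).
- Section 6.3.3.1, multiple imputation with onset MBS in the model: a covariate is missing, so failure again.
- Section 6.3.3.1, complete cases: excluded.
- Section 6.3.3.1, varying response rates: imputed at 0%, 10%, 20% or 30%.

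**3. Size.** Let kA and kP be the numbers of such subjects in the active and placebo arms. The documents give neither, so 4, 8 and 19 (about 1%, 2% and 5% of 380) are assumptions. Everyone else responds at 22% or 12%.
- Scored as failure: active = (380 − kA) × 0.22 / 380; placebo = (380 − kP) × 0.12 / 380.
- Copy from reference, taken as 12% for these subjects in both arms: add kA × 0.12 / 380 and kP × 0.12 / 380.
- Copy-from-reference difference minus failure difference = 0.12 × (kA − kP) / 380. Per subject of imbalance: 0.12 / 380 = 0.00032, or about 0.03 points.

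| kA / kP | Difference, failure (points) | Difference, copy from reference (points) | Gap (points) |
|---|---|---|---|
| 4 / 4 | 9.89 | 9.89 | 0 |
| 8 / 8 | 9.79 | 9.79 | 0 |
| 19 / 19 | 9.50 | 9.50 | 0 |
| 19 / 10 | 9.22 | 9.50 | 0.28 |
| 10 / 19 | 10.02 | 9.74 | −0.28 |

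With equal counts the fall from 10 points is common to both rules, since each assumes no drug benefit in these subjects. It is not an effect of the covariate rule. What that rule does is lower each arm's rate by 0.12 × k / 380: 0.13, 0.25 and 0.60 points for k = 4, 8 and 19.

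With equal counts the test still shifts slightly, because lower rates have a smaller binomial variance. At 19 per arm the same power formula gives 88.0% with failure scoring and 86.9% with copy from reference, ignoring between-imputation variance.

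**The case against.** The case for leaving the text alone is substantial, and most of it stands as a limit on the point.

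- **Onset MBS is optional.** The list says what the covariates may include, so the statistician can already omit it. That stands: the effect arises only if it is kept. It also means that the set of subjects forced to failure is not settled in advance.
- **Two other analyses cover these subjects.** The complete-case and varying-response-rate analyses use no covariates and both relax NC=F. That stands: the gap is confined to the multiple imputation.
- **The group is narrow.** Dosing before answering the diary questions is contrary to protocol Section 7.2.2. A subject who gives no dosing time has no onset pain level and is out of mITT. The point further needs a missing 2-hour score. That stands, although SAP Section 6.2.5.1 does plan to tabulate subjects who dosed before using the diary.
- **Imbalance is not to be expected.** Dosing before opening the diary precedes any drug effect, so randomization should balance it. This holds for early dosing. A missing 2-hour entry is a post-dose event, so imbalance cannot be excluded, but nothing in the documents points to it.

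A reader might also take the parenthesis literally and infer that an observed pain-free subject without onset MBS is turned into a failure. The context does not support that. The parenthesis sits in a sentence about imputing missing 2-hour data, and the bullet opens with the same purpose. This is a wording ambiguity worth closing, not a rule that discards observed responses.

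**Conclusion.** The point holds in a limited form. In the pain-freedom multiple imputation, mITT subjects who lack both a 2-hour score and a covariate are scored as failures. If onset MBS is in the model, the diary design guarantees that the covariate is missing for those who reported dosing before they opened it. For them this analysis repeats NC=F.

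The expected effect is small. Arm-level rates are lower by 0.13 to 0.60 points for 4 to 19 affected subjects per arm. The treatment difference moves by about 0.03 points per subject of imbalance, in either direction. These figures rest on 380 per arm, the SAP's planning rates, a 12% imputed rate in both arms, and assumed counts.

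It would go too far to conclude that NC=F is untested for these subjects, or that the principal result is affected. The two other sensitivity analyses test it, and neither the principal analysis nor its decision rule uses the covariates.

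**What to change.** In SAP Section 6.3.3.1, change both parts of the sentence. Deleting only the parenthesis would leave the main clause restricting imputation to subjects with complete covariates, and the rest would have no rule.

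1. State that, after RM=F, every missing 2-hour pain score is imputed.
2. Fix the covariate list in place of the permissive wording. Either drop onset MBS from the pain-freedom model, or impute missing covariates (onset MBS, historical attack frequency) in the same FCS run, a method that can handle incomplete covariates. If onset MBS is dropped, a missing historical attack frequency still needs this treatment.
3. As a clarification, state that an observed 2-hour outcome is changed only by RM=F.
4. SAP Section 6.3.3.2 refers back to this section for details, so keep its separate rule that a missing onset MBS is a failure for MBS freedom.

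The cost is a short SAP edit and a small change to the imputation program. No new data are needed, and the principal analysis is unchanged.

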### 6.3.3.2 MBS Freedom at 2 Hours Post-Dose

MBS freedom is defined as the MBS reported at on-study migraine attack onset and being absent at a single time point post-dose, e.g., subjects who report nausea as the MBS at onset before taking study drug and have nausea absent at 2 hours post-dose.

For the co-primary endpoint, subjects who meet both of the following criteria will be classified as responders:

- MBS reported at migraine attack onset before taking study drug and being absent at 2 hours post-dose, i.e., in the 2-hour post-dose analysis window
- No intervening rescue medication taken at or before 2 hours-dose, i.e., rescue medication start date/time missing or > {eDiary finding date/time in the 2-hour post-dose analysis window}.

Subjects who are not classified as responders and have any of the following will be classified as failures:

- MBS missing at on-study migraine attack onset (see Section 7.6.3.2)
- Intercurrent event: Rescue medication taken at or before 2 hours post-dose (RM=F) i.e., (rescue medication start date/time study drug start date/time) ≤ 135 minutes, the upper bound of the 2-hour post-dose analysis window (see Section 7.5)
- MBS present at 2 hours post-dose, e.g., nausea reported as MBS at onset and nausea present in the 2-hour post-dose analysis window
- MBS missing at 2 hours post-dose (NC=F), e.g., nausea reported as MBS at onset and nausea status missing in the 2-hour post-dose analysis window.

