3 STUDY ENDPOINTS

3.1 Primary

Pain freedom will be assessed using the number of evaluable subjects that report no pain at 2 hours post-dose. Pain will be measured on a 4 point Likert scale (0=none, 1=mild, 2=moderate, 3=severe).

Freedom from the most bothersome symptom (MBS) will be assessed using the number of evaluable subjects that report the absence of their MBS at 2 hours post-dose. The MBS (nausea, phonophobia or photophobia) will measured using a binary scale (0=absent, 1=present).

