¹ Screening Phase will be 3 - 28 days. Subject should be entered in the IWRS once they sign the informed consent form to obtain their study subject identification code.

²The **Baseline**/ **Randomization Visit** may only occur *after* all screening procedures are completed and the subject meets all inclusion/exclusion criteria. If the subject does not meet all eligibility requirements, the subject should be screen failed in the IWRS.

³ Subjects will use their assigned eCOA handheld device to answer questions about their migraine symptoms upon experiencing a moderate or severe migraine headache. The subject will administer study drug or matching placebo if the following criteria are met: 1) the headache remains moderate or severe; 2) the subject has completed all required migraine assessment questions in the handheld, including their current most bothersome migraine symptom, and 3) the subject has not already taken prohibited medications (see protocol section 5.4).

⁴ Subjects should keep track of their concomitant and rescue medications on the appropriate study paper diary provided throughout the study. These diaries should be returned to the investigational site for review and electronic data capture (EDC) entry.

⁵ The randomization visit is considered day 1 out of the 45 days subjects have to treat and report a migraine in their handheld device. Subjects will be randomized in the IWRS and will be stratified by answering "yes" or "no" to prophylactic migraine medication use in the IWRS.

⁶Nasal inspection – The nasal passages and turbinates will be visually inspected with a nasal speculum or otoscope at the screening, baseline and end of treatment visits to detect evidence of nasal inflammation or edema.

⁷ Height will only be captured at the Screening Visit. Weight, body temperature, respiratory rate, blood pressure and heart rate will be collected at all time points where indicated. Sitting arterial systolic and diastolic blood pressure and pulse rate will be measured.

- ⁸ SAEs are reported from the time of signed informed consent and non-serious AEs are reported from baseline. All ongoing non-serious AEs and SAEs will be followed to resolution or until the Investigator deems there will be no further status change. SAEs that occur during the treatment period should be reported to site in real time. Non-serious AEs that occur during the treatment period should be reported to the site at the EOT.

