# 2.3.1 Primary Objective Estimands

Both co-primary objectives have efficacy endpoints. The estimands corresponding to the co-primary objectives are shown in Table 1.

For each objective, intercurrent events will be handled with a composite strategy described in Section 2.3. The population summary is the difference in the percentage of subjects achieving the endpoint between each BHV-3500 treatment group (5 mg, 10 mg, 20 mg) and the Placebo treatment group.

Table 1: Co-Primary Objective Estimands

Objective	Pain Freedom at 2 hours post-dose
Endpoint	Percentage of subjects with no pain at 2 hours post-dose and no intervening rescue
-	medication taken at or before 2 hours post-dose
Objective	MBS Freedom at 2 hours post-dose
Endpoint	Percentage of subjects with (1) MBS reported at on-study migraine onset before taking
	study drug, (2) MBS absent at 2 hours post-dose, (3) and no intervening rescue
	medication taken at or before 2 hours post-dose

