# 6.3.4.4 Freedom from Photophobia, Phonophobia or Nausea at 2 Hours Post-

Freedom from each symptom (nausea, phonophobia, photophobia) at 2 hours post-dose will be assessed separately.

Symptom freedom is defined as a symptom absent at a single time point post-dose for subjects with the symptom present at on-study migraine attack onset. Thus, all analyses of symptom freedom will be based on mITT subjects with the symptom present at on-study migraine attack onset (see Section 7.6.3.2), e.g., nausea freedom at a post-dose time point will be based on subjects with nausea present at onset.

Symptom freedom outcomes at 2 hours post-dose will be summarized by treatment group (see Section 6.3.5.2).

Treatment group comparisons of the percentage of subjects with symptom freedom at 2 hours post-dose will use analogous methods as the principal analysis of the co-primary endpoint of pain freedom with NC=F and RM=F (see Section 6.3.3.1).

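### The co-primary MBS rule does not require the named symptom to be present at onset, so a subject recorded without it before dosing can count as a responder

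*SAP*

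**What the plan says.** Protocol 3.1 defines the endpoint by the number of evaluable subjects who "report the absence of their MBS at 2 hours post-dose". SAP Table 1 (section 2.3.1) adds that the MBS must be one "MBS reported at on-study migraine onset before taking" study drug. SAP 6.3.3.2 makes a subject a responder on "MBS reported at migraine attack onset before taking study drug and being absent at 2 hours post-dose" together with no rescue by 2 hours. The MBS outcome categories in SAP 6.3.5.2 follow the same rule. The only failure category that refers to onset is "MBS missing at on-study migraine attack onset".

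Before dosing, the subject must complete the handheld questions, "including their current most bothersome migraine symptom" (Protocol Table 1, footnote 3). SAP 7.6.3.2 lists "MBS (nausea, phonophobia, photophobia) in the Migraine Report only" as one item, and the present/absent status of each of the three symptoms as separate items. No option for none is listed. The mITT definition (SAP section 3) requires moderate to severe pain at onset but no associated symptom.

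The symptom-specific secondary endpoints are handled differently. SAP 6.3.4.4 states that "all analyses of symptom freedom will be based on mITT subjects with the symptom present at on-study migraine attack onset", and SAP 6.3.5.2 lists the remaining subjects as not evaluable for that symptom.

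**The concern.** Naming a symptom and having it are two separate data items, and the co-primary rule uses only the first. Freedom from a symptom that was already absent before dosing says nothing about treatment. A subject in that position meets both responder criteria and no failure criterion, while the secondary analysis of the same symptom leaves the subject out.

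A dose must succeed on both co-primary endpoints (SAP 6.1.2), so anything that adds treatment-independent responders to MBS freedom weakens a test that has to be won. None of the three planned MBS sensitivity analyses addresses this, because all of them concern missing data. The planned 3 x 3 table (SAP 6.2.4.6) sets historical MBS against on-study MBS, not named MBS against its onset status.

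**Working it through.** **Classification.** Take a subject who names nausea before dosing, has nausea recorded absent at onset and at 2 hours, and takes no rescue.

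- SAP 6.3.3.2, responder criteria: MBS named before dosing and absent at 2 hours, yes; no rescue, yes.
- SAP 6.3.3.2, failure criteria: MBS missing at onset, no; rescue, no; MBS present at 2 hours, no; status missing at 2 hours, no.
- Result: responder on the co-primary, but not evaluable for nausea freedom under SAP 6.3.4.4 and 6.3.5.2.

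**Inputs from SAP section 5.** n = 380 per arm; MBS freedom 45% and 32%; pain freedom 22% and 12%; alpha = 0.0167, taken as two-sided because that reproduces the stated power (z = 2.393).

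**Power formula** (pooled chi-square, with p̄ the mean of p1 and p2):

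Power = Φ{ [ |p1 − p2| − z√(2p̄(1−p̄)/n) ] / √( [p1(1−p1) + p2(1−p2)]/n ) }

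**The plan's own figures.** For MBS: (0.13 − 2.393 × 0.03530) / 0.03498 = 1.30, so power is 90.3% (stated: 90%). Pain freedom gives 90.1% (stated: 90%). The product is 81.4% (stated: roughly 80%). The sample size calculation reproduces.

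**Illustration.** The documents do not give q, the share of each arm whose named MBS was absent at onset, so 2%, 5% and 10% are assumptions. I also assume that 45% and 32% hold among symptom-present subjects, that q is the same in each arm, and that 95% of absent-at-onset subjects meet the responder rule at 2 hours.

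- Rule as written: p = (1−q) × 45% or 32%, plus 0.95q, n = 380
- Counted as failures: p = (1−q) × 45% or 32%, n = 380
- Restricted to symptom-present subjects: p = 45% or 32%, n = 380(1−q)

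| q | Rule as written | Counted as failures | Restricted |
|---|---|---|---|
| 2% | 46.0% vs 33.3%, 12.7 points, power 88.6% | 44.1% vs 31.4%, 12.7 points, power 89.3% | n = 372, 13 points, power 89.6% |
| 5% | 47.5% vs 35.2%, 12.4 points, power 85.8% | 42.8% vs 30.4%, 12.4 points, power 87.5% | n = 361, 13 points, power 88.6% |
| 10% | 50.0% vs 38.3%, 11.7 points, power 80.5% | 40.5% vs 28.8%, 11.7 points, power 84.2% | n = 342, 13 points, power 86.7% |

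Under the written rule and the failure rule alike, the difference is (1−q) × 13 points, because the 0.95q term cancels. The failure rule gains 0.6, 1.7 and 3.7 points of power through smaller variance alone. Only restriction keeps the 13-point difference.

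Under the SAP's independence assumption, joint power with the rule as written is 79.9%, 77.3% and 72.6%, against 81.4% at q = 0.

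**The case against.** The strongest reply is that these subjects may be rare or may not exist. Protocol 4.3.2 asks for the symptom that is currently most bothersome, which implies that it is present. The eDiary screens are not in the documents, and the device may offer only symptoms already marked present. This stands: q has no support in either document, and a documented device check would close the point.

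Second, 45% and 32% are given as rates for the endpoint, which could mean the endpoint as written. On that reading the planned power is 90.3% whatever q is, and nothing is lost against plan. This also stands, so the table shows sensitivity to an assumption and is not an error in the sample size.

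Third, response is not automatic. The subject needs an observed 2-hour status, no rescue, and a symptom that does not emerge. Subjects who dosed before using the eDiary have no MBS collected and are already failures.

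Fourth, SAP 6.3.4.4 does not contradict 6.3.3.2. The protocol limits the symptom-specific secondary endpoints to subjects with the symptom at baseline and sets no such limit on the co-primary. Onset MBS and onset status also appear in the planned tables and by-subject listings, so cases could be found afterwards. That is true, but finding them after unblinding would leave a post hoc choice about a co-primary definition.

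A reader might infer that the rule favours BHV-3500 or inflates type I error. The documents do not support this. The MBS is named before dosing in a randomized, blinded trial, so such subjects are expected equally in all arms and the effect is conservative.

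**Conclusion.** The classification gap is real on the text. SAP Table 1, 6.3.3.2 and 6.3.5.2 make a subject a co-primary responder for a symptom recorded absent before dosing, and no check that prevents this is described. The consequence, if such subjects occur, is higher MBS rates in all arms and a diluted difference. Under the stated assumptions, shares of 2% to 10% take the difference from 13 points to between 12.7 and 11.7, and MBS power from 90.3% to between 88.6% and 80.5%.

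Two stronger readings should be avoided. The trial has not been shown to lose up to ten points of power, since that needs both an unsupported 10% share and the reading of 45% and 32% as symptom-present rates. Nor does counting these subjects as failures undo the dilution: it corrects the classification and recovers a little power, but the difference stays at (1−q) × 13 points. The point is minor, and it is best settled before unblinding.

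**What to change.** Before unblinding:

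1. Add to the responder rule in SAP 6.3.3.2, and correspondingly to Table 1 and 6.3.5.2, that the symptom named as MBS was recorded present at on-study attack onset. Handle absent-at-onset subjects as failures, in the same way as a missing MBS at onset. This keeps every mITT subject in the analysis.
2. Add a sensitivity analysis restricted to subjects whose named MBS was present at onset. The subset is defined before dosing, and it keeps the 13-point difference under the assumptions above.
3. Tabulate named MBS against its onset status by arm.
4. If the eDiary already prevents naming an absent symptom, say so in the SAP.

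All of this uses data already collected. The cost is slightly lower MBS rates in all arms if such subjects exist, plus one extra analysis and one table.
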